Subject Population: Subjects with AIC and who are eligible to undergo cardiac catheterization/NOGA.	

Design and Investigational Plan: Approximately thirty-six (36) subjects (including six actively treated lead-in participants and up to thirty-one randomized clinical trial participants) will be enrolled. The six subjects participating in the open-label lead-in will receive allo-MSC as described below in Group A. The remaining approximately subjects will be randomized 1:1 to one of two treatment strategies:
 
 ○ Group A (15 subjects): 100×10^6 (100 million) allo-MSCs delivered in twenty 0.4 ml injections. ○ Group B (15 subjects): 20 injections of 0.4 ml cell-free Buminate solution. • For patients randomized to Group A, the allo-MSCs will be derived from allogeneic bone marrow isolated from normal, healthy donors by standard iliac crest aspiration. • Cells or placebo will be administered via the NOGA Myostar injection system. • The injections will be administered transendocardially during cardiac catheterization using the NOGA Myostar Injection System. Injections will be targeted throughout the left ventricle based on NOGA mapping and assessment of scar / fibrosis. • All consented and eligible subjects will have study product injection within 45 days of signing informed consent. • Following cardiac catheterization and allo-MSC or placebo injections, subjects will be followed at day 1, week 1, and months 1, 6, and 12 to complete all safety and efficacy assessments. 	

Eligibility Criteria:
 
Inclusion Criteria
 
To participate, a subject MUST:
 
 1. Be ≥ 18 and < 80 years of age 2. Be a cancer survivor with diagnosis of AIC 3. Have an LVEF $\leq 45\%$ by cMRI 4. Be in NYHA class II-III 5. Have received the initial diagnosis of AIC at least six months earlier and be on stable, optimally-tolerated therapy with beta-blockers, ACE inhibitors/ARBs, and/or aldosterone antagonists for 3 months, unless contraindicated 6. Have a period of at least two years of clinical cancer-free state* and low likelihood of recurrence (a five-year risk of recurrence estimated at 30% or less), as determined by an oncologist, based on tumor type, response to therapy, and negative metastatic work-up at the time of diagnosis *exceptions to this are carcinoma in situ or fully resected basal and squamous cell cancer of the skin. 7. Be a candidate for cardiac catheterization 	

Exclusion Criteria
 
To participate, a subject MUST NOT HAVE:
 
 1. A life expectancy <12 months 2. A CT scan or baseline cardiac MRI showing new tumor or suspicious lymphadenopathy raising concern of malignancy 3. Presence of obstructive CAD as determined via imaging within 5 years prior to study enrollment provided there have been no symptoms or evidence of CAD since the test (see section 4.1 for 	

(imaging guidance))

4. Had a previous myocardial infarction
5. A history of radiation therapy AND evidence of constrictive physiology and/or evidence of other patterns of non-ischemic cardiomyopathy on cardiac MRI (e.g., amyloidosis, sarcoidosis, hemochromatosis, pure radiation-induced cardiomyopathy, etc.) not consistent with AIC being the dominant etiology of heart failure
6. Valvular heart disease including 1) mechanical or bioprosthetic heart valve; or 2) severe valvular (any valve) insufficiency/regurgitation within 12 months of consent
7. Aortic stenosis with valve area $\leq 1.5\text{cm}^2$
8. A history of LV reduction surgery or cardiomyoplasty
9. Evidence of cardiogenic shock
10. A history of ischemic or hemorrhagic stroke within 90 days of baseline testing
11. Liver dysfunction during baseline testing, as evidenced by enzymes (e.g., AST, ALT, alkaline phosphatase) greater than 3 times upper limit of normal
12. Diabetes with poorly controlled blood glucose levels ($\text{HbA1c} > 8.5\%$)
13. An underlying autoimmune disorder or current immunosuppressive therapy (e.g., chronic corticosteroid, rheumatologic or immune modulating therapy) or likelihood of use of immunosuppressive therapy during participation in the trial (*medications will be considered on a case by case basis*)
14. A baseline eGFR $<35 \text{ ml/min}/1.73\text{m}^2$
15. A contrast allergy that cannot adequately be managed by premedication
16. Received gene or cell-based therapy from any source within the previous 12 months
17. A hematologic abnormality during baseline testing as evidenced by hemoglobin $< 9 \text{ g/dl}$; hematocrit $< 30\%$; absolute neutrophil count $< 2,000$ or total WBC count more than 2 times upper limit of normal; or platelet values $< 100,000/\text{ul}$
18. Evidence of active systemic infection at time of study product delivery
19. HIV and/or active HBV or HCV
20. Coagulopathy (INR > 1.5) not due to a reversible cause (e.g., warfarin and/or Factor Xa inhibitors) (see Section 6.4 re: injection procedure and anticoagulation therapy) *Note: Subjects who cannot be withdrawn from anticoagulation will be excluded.*
21. Presence of LV thrombus (*see guidance in Section 6.6.3*)
22. Presence of a pacemaker and/or ICD generator with any of the following limitations/conditions:
 - manufactured before the year 2000
 - leads implanted < 6 weeks prior to consent
 - non-transvenous epicardial or abandoned leads
 - subcutaneous ICDs
 - leadless pacemakers
 - any other condition that, in the judgment of device-trained staff, would deem an MRI contraindicated
23. Pacemaker-dependence with an ICD (*Note: pacemaker-dependent candidates without an ICD are not excluded*)
24. A cardiac resynchronization therapy (CRT) device implanted < 3 months prior to consent
25. Other MRI contraindications (e.g. patient body habitus incompatible with MRI)
26. An appropriate ICD firing or anti-tachycardia pacing (ATP) for ventricular fibrillation or ventricular tachycardia within 30 days of consent
27. Ventricular tachycardia ≥ 20 consecutive beats without an ICD within 3 months of consent, or symptomatic Mobitz II or higher degree atrioventricular block without a functioning pacemaker within 3 months of consent
28. A history of drug abuse (use of illegal "street" drugs except marijuana, or prescription medications not being used appropriately for a pre-existing medical condition) or alcohol abuse (≥ 5 drinks/day for > 3 months), or documented medical, occupational, or legal problems arising from the use of

alcohol or drugs within the past 24 months

29. Cognitive or language barriers that prohibit obtaining informed consent or any study elements (interpreter permitted)
30. Participation (currently or within the previous 30 days) in a cardiac related investigational therapeutic (including stem cell based therapies) or device trial
31. Pregnancy, lactation, plans to become pregnant in the next 12 months, or is unwilling to use acceptable forms of birth control during study participation
32. Any other condition that, in the judgment of the Investigator or Sponsor, would be a contraindication to enrollment, study product administration, or follow-up

Primary Endpoints

Safety: To demonstrate the relative safety of allo-MSCs when compared with placebo, the following safety data will be collected and analyzed by therapy group between baseline and a) 6 months and b) 12 months:

1. Major adverse cardiac events (MACE) including: death, hospitalization for worsening heart failure (HF), and/or other exacerbation of HF (non-hospitalization)
2. Other significant clinical events including: non-fatal stroke, non-fatal myocardial infarction, coronary artery revascularization, ventricular tachycardia/fibrillation, pericardial tamponade, infectious myocarditis, hypersensitivity reaction, neoplasm, and/or any other potential deleterious late effects detected and corroborated by clinical presentation, laboratory investigations, image analysis, and when necessary with biopsy from suspected target sites in the body
3. All adverse events (AEs) at least grade 2 in severity

Feasibility: To assess the practicality of study procedures, the following measures will be reported.

The number and percent of subjects who:

1. Have events between randomization and SPI that preclude the subjects from getting SPI
2. Receive less than 20 injections during the SPI procedure
3. Do not receive the intended dose of cells (100 million), reason, and actual dose delivered
4. Have at least one cardiac MRI endpoint measure that is uninterpretable due to issues related to the device, including, but not limited to, inability to undergo the procedure
5. Fail to complete follow-up

Secondary Endpoints

Prospectively Declared Efficacy Endpoint Measures:

To explore whether allo-MSCs produce a trend toward improved LV function and functional status when compared with placebo, the following domains and measures will be evaluated:

- Myocardial evaluations by cMRI over time:
 - Function:
 - Change in LVEF
 - Change in global and regional strain (HARP MRI)
 - Structure:
 - Change in LVEDVI
 - Change in LVESVI
 - Change in LV Sphericity Index
 - Morphology:
 - Change in area of injury (e.g., inflammation, edema, fibrosis)
- Functional capacity over time:
 - Change in exercise tolerance (6MWT)
 - Change in MLHF Questionnaire (subject reported)
- Clinical outcomes over time:
 - MACE
 - Cumulative days alive and out of hospital
- Biomarkers over time:
 - Change in NT-proBNP

Duration of Study Follow-Up: Following discharge from the hospital, subjects will be assessed at week 1, and months 1, 6, and 12 (including assessment for cancer recurrence).

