Priority for selecting the 20 injection sites will be based upon the objective of delivering the study product in a minimum of four myocardial segments according to the AHA 17 segment polar map) selected by the investigator to be a territory which is: a) safely treatable with low risk of perforation or other complications; b) avoiding the true LV apex and other areas known to be < 6 mm in myocardial thickness, and avoiding the left bundle branch site of earliest activation; c) clinically important based on viability assessments provided below; and, d) accessible with the tip of the selected MyoStar catheter.

The NOGA map obtained will be unique in that it will display heterogeneous distribution of unipolar voltage in the LV, typical of patients with dilated cardiomyopathy. This is thought to represent areas of relative fibrosis and will serve as the basis for selection of the target injection area. The operator will proceed to delineate an injection area using the criteria mentioned above and ideally select injection sites that demonstrate intermediate level unipolar voltage (4 to 8mV). This range can be expanded to include areas with unipolar voltage of up to 12mV if necessary.

Sites for injection should satisfy the following criteria: (1) perpendicular position of the catheter to the LV wall; and (2) loop stability < 4mm. Ideally the majority of injections will be placed at a site with a voltage threshold of ≥ 4mV and ≤ 8mV. *When selecting sites for injection generally those with a voltage < 4mV will be avoided unless there are no higher unipolar voltage values present on the unipolar voltage map.*

Each of the 20 injections will contain either 0.4 ml of cell suspension with 5 million allo-MSCs per injection site for the active cell treatment arm or 0.4 ml of cell-free Buminate solution for the placebo group. For the final injection, 0.1 cc of saline should be placed in the catheter and injected. This will allow the 0.1 cc already in the catheter (from priming) to be administered into the myocardium, constituting the 20th injection. Each injection should be infused over 60 seconds.

Sites of injection will be marked and recorded by a solid circular tag on the NOGA map accompanied by a reference to injection number and presence or absence of needle-induced extrasystole. Sites of injection may also be recorded on cine fluoroscopy, and demarcated as a dot with the corresponding injection series number on overlay tracings in both RAO and LAO projections.

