
After the injection procedure, subjects will be monitored overnight. A 2-D echocardiogram will be performed post SPI (within 6 hours). Additional echocardiographic assessments for pericardial effusion will be done only as clinically indicated. Troponin I or T will be collected 8 (+/- 2) hours post-injection catheter procedure and again prior to discharge. An analysis of the impact of biomarker elevations on measures of LV function and MACE will be carried out. We believe this will demonstrate that biomarker elevations are not related to study outcomes.

CONFIDENTIAL AND PROPRIETARY

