5.5 Circumstances That May Affect Study Product Delivery

If any of the following symptoms occur before or during SPI, they could indicate a serious clinical deterioration. If any of the following events/symptoms occurs, the procedure should be temporarily halted and the patient should be reevaluated for suitability to continue with the treatment under investigation:

1. Hypotensive episode defined as a sustained drop in blood pressure exceeding 20 mmHg not responsive to fluid administration
2. Hemodynamically significant arrhythmia requiring antiarrhythmic therapy
3. Two episodes of sustained ventricular tachycardia/ventricular fibrillation requiring cardioversion
4. Hemodynamically unstable
5. Fever (temperature increase to $\geq 100.4^{\circ}\text{F}$)
6. Cardiac perforation
7. Clinical signs and symptoms indicating a cerebrovascular accident

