6.0 CLINICAL AND LABORATORY PROCEDURES

6.1 Schedule of Procedures (Table 3)

SENECA Study Procedure	BSL	D0 (SPI)	D1	Wk1 (+/-3 days)	M1 (+/-7 days)	M6 (+/-30 days)	M12 (+/-30 days)	M24 (+/-30 days) Call ₇
Informed Consent	X							
Complete Medical History	X							
Physical Exam	X	X	X	X	X	X	X	
Vital Signs	X	X ₁	X	X	X	X	X	
Adverse Events	X	X	X	X	X	X	X	
Con Medications	X	X	X	X	X	X	X	
NYHA	X				X	X	X	
MLHFQ	X					X	X	
12-lead ECG	X	X ₂	X ₂	X		X	X	
Stress Echo	O							
2D Echoes		X ₂						
Telemetry		X ₃						
Labs and Biomarkers (PB)₄	X	X	X	X	X	X	X	
Cardiac MRI	X					X	X	
ICD Interrogation₅	X	X				X	X	
6 Minute Walk	X					X	X	
Randomization	X							
Catheterization / NOGA		X						
Temp. Log			X ₆					

Telephone Interview								X
---------------------	--	--	--	--	--	--	--	---

O= indicates optional test; dependent upon available imaging in the patient chart to assess CAD.

Baseline testing, randomization, and SPI will take place within 45 days of ICF.

1. Subjects will have assessments of vitals (BP, temperature, pulse rate) pre- and post-procedure.
2. ECGs will be performed within 6 hours following the catheterization procedure and again before discharge; a 2-D echocardiogram will be performed post SPI (within 6 hours).
3. Subjects will be monitored on simple telemetry up to 24 hours post-procedure or until discharge, whichever is sooner.
4. See section 6.3 for specific tests done at each time point.
5. ICD interrogation (if applicable) done before and after every MRI as part of MRI protocol as well as before the SPI procedure.
6. Temperature log 2x/day x 7 days.
7. 24-Month contact is a telephone visit only.

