7.3.1 Severity Assessment

The DCC uses the Common Terminology Criteria for Adverse Events (CTCAE), version 4.0, for detailed descriptions of Severity Grades. The CTCAE schema is classified by body system and event using the MedDRA hierarchy and provides descriptions of events that qualify under each severity rating.

The following table contains general descriptions of Adverse Event Severity Grades.

Please note: Grade 1 (Mild) AE/SARs are not entered in the electronic CRF in the CCTRN database.

Severity Grade	Description
1	Mild. Asymptomatic or mild symptoms; clinical or diagnostic observations only; intervention is not indicated.
2	Moderate. Minimal, local, or non-invasive intervention indicated or limiting activities of daily living (i.e. preparing meals, shopping for groceries/clothes, managing money, using telephone, etc.)
3	Severe or medically significant but not immediately life-threatening. Hospitalization or prolongation of hospitalization indicated OR disabling OR limiting self-care (e.g. bathing, dressing, feeding self, using toilet, taking medications, etc.)
4	Life-threatening consequences; urgent intervention indicated.
5	Death. Death related to adverse event.

Notice that severity and seriousness are different concepts. For example, a headache may be severe (interferes significantly with subject's usual function) but would not be classified as serious unless it met one of the criteria for SAE/SSARs (see section 7.1.3 above).

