8.3.2.1 Safety Evaluations

To demonstrate the relative safety of allo-MSCs when compared with placebo, the following analyses will be carried out, and the data tabulated and analyzed by therapy group (Fisher's Exact Test) between baseline and a) 6 months and b) 12 months:

1. Major adverse cardiac events (MACE) including death, hospitalization for worsening heart failure (HF), and/or exacerbation of HF (non-hospitalization)
2. Other significant clinical events including non-fatal stroke, non-fatal myocardial infarction, coronary artery revascularization, ventricular tachycardia/fibrillation, pericardial tamponade, infectious myocarditis, hypersensitivity reaction, neoplasm, or any other potential deleterious late effects detected and corroborated by clinical presentation, laboratory investigations, image analysis, and when necessary with biopsy from suspected target sites in the body
3. All adverse events (AEs) at least grade 2 in severity (see section 7.3.1)

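### Silent pericardial effusions and conduction changes found by the scheduled post-injection echo and ECGs may go unrecorded, and treated ones have no named place in the primary safety result

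*Combined protocol and SAP*

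**What the plan says.** The primary safety endpoint has three items, repeated in substance in the Executive Summary, section 3.4.1 and section 8.3.2.1: MACE, other significant clinical events, and all adverse events of grade 2 or higher. Section 8.3.2.1 tabulates them by therapy group, with Fisher's exact test, to 6 and 12 months. Item 2, as worded in the Executive Summary, includes "coronary artery revascularization, ventricular tachycardia/fibrillation, pericardial tamponade, infectious myocarditis, hypersensitivity reaction, neoplasm, and/or any other potential deleterious late effects detected". The list ends with a catch-all for late effects.

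Elsewhere the protocol recognises the procedural hazards:

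- Section 5.4 limits needle depth to avoid injection outside the heart, and asks operators to choose sites while "avoiding the left bundle branch site of earliest activation".
- Section 5.5 lists "Cardiac perforation" among the events that halt the procedure.
- Sections 9.1.2.1 and 9.1.2.3 list perforation with blood around the heart as a risk.
- Sections 5.4 and 6.4 require a 2-D echo within 6 hours of injection. Beyond that, "Additional echocardiographic assessments for pericardial effusion will be done only as clinically indicated".
- Table 3 (section 6.1) states that "ECGs will be performed within 6 hours following the catheterization procedure and again before discharge", and schedules further ECGs at week 1 and months 6 and 12.

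Section 7.2.1 makes a test result an adverse event if it comes with symptoms, needs further diagnostic testing or intervention, or is considered one by the investigator or sponsor. Section 7.3.1 describes grade 1 as "Asymptomatic or mild symptoms; clinical or diagnostic observations only; intervention is not indicated" and says that grade 1 events are not entered in the eCRF.

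**The concern.** Delivery by transendocardial injection is part of the primary objective (section 1.1). The echo and ECGs are the scheduled tests most likely to show mechanical or conduction injury from the needle, and every injected subject has them. Yet the endpoint names only the extreme pericardial event, and no planned analysis uses either test. Section 5.4 does plan an analysis of post-injection biomarker elevations; nothing comparable exists for the echo or ECG.

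At stake is the completeness of the delivery-safety result. A silent effusion or a new asymptomatic bundle branch block could leave no database record, and so could not be tabulated at the end of the trial. The protocol itself uses such information as evidence: Table 1 (section 2.6.3) cites the absence of pericardial effusion as a safety result of an earlier intramyocardial study. As specified, this trial need not produce a comparable figure.

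**Working it through.** The plan states no figure on this point, so there is none to reproduce. The check traces each type of finding through the three safety items and then gives a scale.

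**Tracing the findings**

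| Finding | Item 2 | Item 3 (grade 2 or higher) | In the eCRF? |
|---|---|---|---|
| Tamponade | Named | Yes, if grade 2 or higher | Yes |
| Perforation | Not named | Almost certainly: it halts the procedure (5.5) and is hard to place in grade 1 | Almost certainly |
| Effusion or block that is treated, limits activities or prolongs the stay | Not named | Yes: non-invasive intervention suffices for grade 2, prolonged hospitalization for grade 3 (7.3.1) | Yes, without its own category |
| Effusion or block, asymptomatic and untreated, graded 1 | Not named | No | Not entered (7.3.1) |
| The same, not judged an adverse event under 7.2.1 | Not named | No | Need not be entered |

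The gap in recording is confined to the last two rows. The second and third rows lack only a named category. The catch-all in item 2 speaks of late effects, so it does not clearly cover a finding made within 6 hours of injection.

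**Amount of data without a planned analysis**

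With about 36 injected subjects (section 3.2) and full attendance, there are 36 six-hour echoes. Each subject has 5 scheduled post-injection ECGs (within 6 hours, before discharge, week 1, months 6 and 12), so 5 × 36 = 180. Losses would lower the count of later ECGs; section 3.5 allows for 15% loss to follow-up.

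**Scale, under assumed rates**

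The documents give no rate for such findings. Let p be the true proportion of injected subjects with one. The expected number is 36p, and the chance of at least one is 1 − (1 − p)^36.

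| Assumed p | Expected number | Chance of at least one |
|---|---|---|
| 3% | 36 × 0.03 = 1.1 | 1 − 0.97^36 = 67% |
| 5% | 36 × 0.05 = 1.8 | 1 − 0.95^36 = 84% |
| 10% | 36 × 0.10 = 3.6 | 1 − 0.90^36 = 98% |

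As an example, suppose three subjects had a silent effusion. The full count is 3/36 = 8.3%, with an exact 95% interval of 1.8% to 22.5%. If all three were graded 1 or not judged adverse events, the reported pericardial count would be 0/36, with an exact upper limit of 1 − 0.025^(1/36) = 9.7%.

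**Comparison between arms**

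With 15 per arm, Fisher's exact test gives p = 0.0996 for 4 versus 0 and p = 0.042 for 5 versus 0. Only an extreme split would reach the nominal 0.05 level of section 8.6.

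**The case against.** The strongest reply is that item 3 already does the work. It takes in adverse events of any type from grade 2 upward and is tabulated by arm. A reader might infer from item 2 alone that perforations, effusions and heart block can all drop out of the primary safety result. The documents do not support that: symptomatic or treated cases enter through item 3. A perforation that ended the injections would also appear in the feasibility measures, which count subjects with fewer than 20 injections and give the reason for an incomplete dose. This part of the reply stands in full.

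Second, the table in section 7.3.1 gives general descriptions only and defers to CTCAE v4.0 for detailed grades. Whether a silent effusion or block would be grade 1 cannot be settled from the documents. Section 7.2.1 also lets the investigator or sponsor judge any finding to be an adverse event. This stands too: the gap is conditional.

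Third, item 2 is worded as an inclusive list, and a conduction change first seen at month 6 or 12 might count as a late effect. That helps with late changes but not with those seen within hours.

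Fourth, the DSMB reviews 1-month safety and feasibility data from all six lead-in subjects (section 7.7). This is a real safeguard, but a review for six subjects is not a planned tabulation for all.

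A reader might also infer that the plan would hide a harmful imbalance between arms. That is weak: both arms receive 20 needle injections, so procedural injury is not where a product difference is mainly expected, and the test has little sensitivity at this size.

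**Conclusion.** The point holds in a limited form, as a cheap improvement. Perforation and treated effusions or conduction disturbances are captured but have no named category. Untreated, asymptomatic effusions and conduction changes can go unrecorded, and section 8 plans no analysis that would show them, although the tests that detect them are already scheduled.

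The size cannot be fixed from the documents. The 67% to 98% chance of at least one finding rests on assumed rates of 3% to 10%. The contrast of 0/36 with 3/36 further assumes that all three findings escaped item 3. The conclusion rests on the text of sections 7.2.1, 7.3.1 and 8.3.2.1, with the extent of the gap depending on the event-specific CTCAE grades.

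**What to change.** 1. In the Executive Summary, section 3.4.1 and section 8.3.2.1, name cardiac perforation in item 2 beside tamponade. Leave small silent effusions out of item 2; they should not be relabelled as significant clinical events.
2. In section 8.3.2.1, add a procedural-safety table with two rows:
   - any pericardial effusion on the scheduled post-injection echo, with tamponade as a subset, noting whether effusion was present on the baseline cMRI, because Table 3 schedules no baseline 2-D echo;
   - new bundle branch block, or Mobitz II or higher AV block, on a scheduled ECG compared with the baseline ECG, with ventricular-paced tracings reported as not evaluable, because subjects with pacing devices can enrol.
3. Record both in the eCRF whatever the adverse event grade.
4. Report them by arm and pooled over all injected subjects, lead-in included, with exact 95% intervals. Make the pooled figure the main one, since both arms are injected.

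The cost is endpoint wording, two eCRF fields and one table, with no new test or visit. The drawbacks are local, unstandardised reads (section 5.3 assigns only cMRI to a core laboratory), a baseline for effusion from a different modality and up to 45 days old (section 4.5), and slightly less favourable safety figures.
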